9.3 VARIABLES

The following variables will be considered for the analysis.

The characteristics of patients with a reported significant hypersensitivity /anaphylactic reaction (if available):

- age
- gender
- weight
- description of hypersensitivity/anaphylactic reactions
 - nature of event
 - outcome
 - seriousness
 - medically confirmed
 - event date
 - event severity
 - mild, moderate, severe
 - grade 1 to 5 according to NCI Common Terminology Criteria for Adverse Events
- history of hypersensitivity/ anaphylactic reactions
- history of reported drug exposure

The characteristics of alglucosidase alfa treatment course (if available):

- treatment start date
- number of doses received
- treatment dosage received

The history of immunology testing performed since treatment start:

- any immunology testing
- alglucosidase alfa IgE antibody
- complement activation
- serum tryptase
- alglucosidase alfa IgG antibody

Immunology testing results will be generally reported as titers.

9.4 DATA SOURCES

This study is based on secondary analysis of existing data sources.

The following data sources will be considered:

- Genzyme's Pharmacovigilance adverse event database,
- Genzyme Clinical Specialty Laboratory database.

Reports pertaining to the same patients will be linked across databases using date of birth, initials, and country of origin.

The Genzyme's Pharmacovigilance adverse event database will provide information about patients with a reported significant hypersensitivity /anaphylactic reaction.

The Genzyme Clinical Specialty Laboratory database will provide history of records and results of immunology testing conducted in these laboratories for patients treated with alglucosidase alfa.

9.5 STUDY SIZE

All patients available in the study population will be considered for the analysis.

No assumption will be made on the expected number of patients with spontaneously reported significant hypersensitivity/anaphylactic reaction occurring during alglucosidase alfa treatment course in countries in Europe.

The Table 3 provides expected precision (95% confidence intervals) according to different values of expected prevalence of immunology testing. The expected value of prevalence is not known and a range of potential values is presented in the table below.

Table 3 - 95% confidence intervals according to different values of prevalence of immunology testing

	Prevalence				
Number of patients	50%	75%	85%	90%	95%
50	[35.5- 64.5%] ^a	[60.7-86.2%] ^a	[72.1-93.5%] ^a	[78.2-96.7%] ^a	[84.8-99.1%] ^a
100	[40.2-59.8%]	[66.5-83.5%]	[78.0-92.0%]	[84.1-95.9%]	[90.7-99.3%]
200	[43.1-56.9%]	[69.0-81.0%]	[80.1-89.9%]	[85.8-94.2%]	[92.0-98.0%]
300	[44.3-55.7%]	[70.1-79.9%]	[81.0-89.0%]	[86.6-93.4%]	[92.5-97.5%]

a Exact 95% confidence interval using binomial exact method (Clopper-Pearson exact method)

9.6 DATA MANAGEMENT

For this study, data extractions from Genzyme's Pharmacovigilance adverse event database will be conducted to get reports pertaining to the population of interest.

Data extractions from the Genzyme Clinical Specialty Laboratory database will be conducted on reports pertaining to the population of interest.

These extractions will be combined to serve as analysis data sets for interim and final analyses. The data linkage will be documented.

9.7 DATA ANALYSIS

The analyses will be descriptive and will be made on all patients available in the databases at time of each analysis.

9.7.1 Analysis population:

The primary analysis population will be patients with spontaneously reported significant hypersensitivity/anaphylactic reaction while treated with alglucosidase alfa treatment course in countries in Europe. Patients will be divided by following two groups:

Group 1 (pre-SIP):

- Patients with hypersensitivity/anaphylactic reaction event onset date from 01 September 2012 to 31 August 2015

Group 2 (post-SIP):

 Patients with hypersensitivity/anaphylactic reaction event onset date from 01 October 2015 to 30 September 2018

9.7.2 Determination of patient status on immunology testing:

A patient in Group 1 (or 2) will be considered having undergone any immunology testing (immunology test = Yes) for the respectively period if one of the two conditions is met:

- i) a valid test result is available for at least one of the following tests from Genzyme Clinical Specialty Laboratory database
 - a. alglucosidase alfa IgE antibody,
 - b. alglucosidase alfa IgG antibody,
 - c. complement activation,
 - d. serum tryptase
- ii) the test date is after the alglucosidase alfa treatment start date through the end of the period cutoff (31 August 2015 for Group 1 and 30 September 2018 for Group 2)

Note that patients without a valid test meeting above criteria will be considered without having immunology test performed (immunology test=No). Therefore, there is no missing data for this endpoint.

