9.2 SETTING

The following data sources will be considered:

- Genzyme's Pharmacovigilance adverse event database,
- Genzyme Clinical Specialty Laboratory database (capturing records and results of immunology testing conducted in these laboratories).

Reports pertaining to the same patients will be linked across databases using date of birth, initials and country of origin.

The Genzyme's Pharmacovigilance adverse event database will be used to identify the population of interest for each study period:

• All patients with a spontaneously reported significant hypersensitivity/anaphylactic reaction occurring during alglucosidase alfa treatment course in countries in Europe.

The following criteria will be used to identify patients with a reported significant hypersensitivity/anaphylactic reaction occurring during alglucosidase alfa treatment course:

• cases identified by the Standardized MedDRA Query "Anaphylactic reaction" and "hypersensitivity".

The Genzyme Clinical Specialty Laboratory database will be used to identify the full history of immunology testing since initiation of treatment with alglucosidase alfa in patients identified from the Genzyme's Pharmacovigilance adverse event database.

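### Section 9.7.2 joins its two test conditions with the wrong connective, so read literally a test after 31 August 2015 can count as pre-SIP testing

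*Protocol*

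**What the plan says.** Protocol section 9.7.2 derives the study's only outcome, any immunology testing (yes or no). A patient is coded Yes "for the respectively period if one of the two conditions is met". The conditions are:

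- (i) "a valid test result is available for at least one of the following tests from Genzyme Clinical Specialty Laboratory database", the list being IgE antibody, IgG antibody, complement activation and serum tryptase. No date limit is attached.
- (ii) "the test date is after the alglucosidase alfa treatment start date through the end of the period cutoff", the cutoffs being "31 August 2015 for Group 1 and 30 September 2018 for Group 2". No validity requirement is attached.

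The Note directly below says that "patients without a valid test meeting above criteria will be considered without having immunology test performed".

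Two other statements decide which tests can be in the data. Under section 9.2 the laboratory database "will be used to identify the full history of immunology testing since initiation of treatment with alglucosidase alfa", and no end date is given. Under section 9.7 the analyses "will be made on all patients available in the databases at time of each analysis". Section 12 adds that the December 2018 report covers both periods cumulatively.

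**The concern.** Validity and date are two attributes of one test. Condition (ii) speaks of the test date, which refers back to the test in (i). Making them alternatives turns a joint requirement into an either-or rule, and the Note then describes something different from the rule it explains.

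The consequence that matters is the late test. A valid result from 2016, 2017 or 2018 satisfies (i) on its own, so a Group 1 patient first tested after the revised SIP could be counted as tested before it. The post-minus-pre difference in this prevalence is the protocol's measure of whether the risk minimisation worked (sections 8 and 9.7.5). Raising the pre-SIP figure lowers that difference and can make an effective measure look ineffective. The error is one-sided: at the final data cutoff Group 2 has no later time in which to gain tests.

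**Working it through.** The protocol gives no figure for this point, so there is none to reproduce. The check has a logical part and an illustrative part.

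**Logic.** Each combination for a single test, under the rule as written (either condition) and under the joint reading (both):

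| Valid result | Date in window | Either | Both |
|---|---|---|---|
| no | no | No | No |
| no | yes | Yes | No |
| yes | no | Yes | No |
| yes | yes | Yes | Yes |

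The readings differ in two rows.

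- *In window, not valid.* The rule gives Yes. The Note requires a valid test and gives No. The section contradicts itself.
- *Valid, out of window.* The rule gives Yes. The Note gives No only if meeting the criteria means meeting both. If it is read as meeting whichever criterion suffices, the late test still counts. The Note points to the joint reading without clearly closing this route.

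**Extra time.** From 31 August 2015 to 30 September 2018 is 1126 days: 1126/365.25 = 3.083 years, or 1126/30.4375 = 37.0 months. Group 2's own cutoff is 30 September 2018, so it has no extra time at that date.

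**Size: assumptions, not protocol figures.** Tests occur at a constant rate r per patient-year, the same for every patient. Each Group 1 patient has 4 years on treatment at 31 August 2015 and stays under treatment and testing until 30 September 2018.

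- Prevalence with the cutoff: p = 1 − exp(−4r)
- Prevalence without it: 1 − exp(−7.083r)
- Inflation: (1 − p) − (1 − p)^(7.083/4) = (1 − p) × [1 − (1 − p)^0.7707]

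Over the range of prevalences in the protocol's Table 3:

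| Group 1 prevalence with cutoff | Inflation (points) |
|---|---|
| 50% | 0.50 × (1 − 0.586) = 20.7 |
| 75% | 0.25 × (1 − 0.344) = 16.4 |
| 85% | 0.15 × (1 − 0.232) = 11.5 |
| 90% | 0.10 × (1 − 0.170) = 8.3 |
| 95% | 0.05 × (1 − 0.099) = 4.5 |

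By assumed rate:

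| r per patient-year | With cutoff | Without | Inflation (points) |
|---|---|---|---|
| 0.05 | 18.1% | 29.8% | 11.7 |
| 0.1 | 33.0% | 50.8% | 17.8 |
| 0.2 | 55.1% | 75.7% | 20.7 |
| 0.4 | 79.8% | 94.1% | 14.3 |

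The model's maximum is 20.7 points, at a prevalence of about 52%.

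**Effect on the difference: a second illustration, also assumed.** Take 100 patients per group, true prevalence 50% before and 65% after, and let a share s of the untested Group 1 patients have a later valid test. The apparent Group 1 prevalence is 0.50 + 0.50s. The 95% interval is the difference ± 1.96 × √[p1(1 − p1)/100 + p2(1 − p2)/100].

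| s | Group 1 | Difference (points) | 95% CI |
|---|---|---|---|
| 0 (both conditions) | 50% | 15 | 1.5 to 28.5 |
| 10% | 55% | 10 | −3.5 to 23.5 |
| 20% | 60% | 5 | −8.4 to 18.4 |
| 30% | 65% | 0 | −13.2 to 13.2 |

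**The case against.** The strongest reply is that the intent can be recovered. The lead sentence ties the status to the patient's own period, condition (ii) refers back to the test in (i), and group-specific cutoffs would have little purpose if validity alone sufficed. A careful programmer would probably require both conditions, and no bias would arise. That stands as a statement of intent. It does not repair the operative sentence, which says the opposite and which the Note does not plainly override for late tests.

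A reader might infer more than the protocol supports:

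- *Tests without a valid result will count.* The Note requires a valid test on any reading and largely closes this route. What remains is a contradiction between rule and Note.
- *Tests before treatment will count.* Section 9.2 limits the laboratory history to testing since treatment start, and section 9.3 defines the variable the same way. Such tests should not reach the rule.
- *Group 1 will change at every annual report.* No section says that Group 1's laboratory history is extracted again each year. Section 9.6 and the cumulative final report make it plausible, no more. If it were extracted only once, with data to 30 September 2016 (396 days, 1.084 years), the same model at r = 0.2 gives 1 − exp(−0.2 × 5.084) = 63.8% against 55.1%, about 9 points.
- *The difference is always pulled toward zero.* It is lowered. Whether that brings it nearer zero depends on the sign and size of the true difference.

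**Conclusion.** The point holds. The protocol states a derivation rule for its only outcome that, followed as written, gives a wrong result for late tests in Group 1 and contradicts its own Note for in-window tests without a valid result. This is a wrong rule, so it is not a detail that could be left to an analysis plan.

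If the literal rule were programmed and later Group 1 tests were in the extract, pre-SIP prevalence would be too high and the post-minus-pre difference too low. Under the model above that is about 5 to 21 points over Group 1 prevalences of 95% to 50%, and about 12 points at a rate of 0.05 per patient-year, where prevalence is only 18%. A reader might take 21 points as the expected bias. It is the top of an assumed model, and it is impossible at a prevalence of 85% or more, where at most 15% of patients are untested. Discontinuation, death or rates that differ between patients would reduce the figures. If the code already requires both conditions, the bias is nil and only the text is wrong.

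**What to change.** In section 9.7.2, replace the either-or clause by: *if at least one test meets both conditions: (i) a valid result and (ii) a test date after treatment start through the period cutoff*. State that both must hold for the same test record, so that a valid late test and an in-window test without a valid result cannot be combined into a Yes. The Note then agrees with the rule.

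Check the derivation code against the corrected sentence, in particular that Group 1 tests dated after 31 August 2015 are excluded at every report. The cost is one sentence and a code check. No figure stated in the protocol changes.

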4 SYNOPSIS

Title

Prevalence of immunology testing in patients treated with alglucosidase alfa with significant hypersensitivity/anaphylactic reactions

Version 3.0

As part of its assessment, PRAC requested revision of the safety information packet (SIP) to improve readability and contents and to assess effectiveness of the revised material in terms of evaluation of the process and evaluation of the outcomes.

This study is focused on evaluation of the outcomes, through the evaluation of the percentage of immunology testing in patients experiencing significant hypersensitivity/anaphylactic reactions.

Research question and objectives

This study aims to determine the prevalence of patients treated with alglucosidase alfa with significant hypersensitivity/anaphylactic reactions who undergo immunology testing. The difference in prevalence of testing between the two periods of 3 years before and after the implementation of the revised SIP (version 8.2) will be assessed as a measure of effectiveness of risk minimization measures.

Study design

Cross-sectional study; repeated analyses will be done pre- and post-implementation of the revised SIP using pre-existing data.

Population

 This study will be conducted using existing data sources recording both cases of significant hypersensitivity/anaphylactic reactions in the Genzyme's Pharmacovigilance adverse event database and routine performance of immunology testing in the Genzyme Clinical Specialty Laboratory database since treatment start.

The following population will be considered:

- All patients treated with alglucosidase alfa with a spontaneously reported significant hypersensitivity/anaphylactic reaction during the study period in countries in Europe.

Variables

The outcome will be the history of any immunology testing since treatment start as well as subtypes of testing performed in patients with a reported significant hypersensitivity/anaphylactic reaction:

- alglucosidase alfa IgE antibody
- complement activation
- serum tryptase
- alglucosidase alfa IgG antibody

Data sources

The following data sources will be considered:

- Genzyme's Pharmacovigilance adverse event database,
- Genzyme Clinical Specialty Laboratory database (capturing records and results of immunology testing conducted in these laboratories).

Reports pertaining to the same patients will be linked across databases using date of birth, initials and country of origin.

Study size

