8 RESEARCH QUESTION AND OBJECTIVES

This study aims to determine the prevalence of patients treated with alglucosidase alfa with significant hypersensitivity/anaphylactic reactions who undergo immunology testing. The difference in prevalence of testing between the two periods of 3 years before and after the implementation of the revised SIP (version 8.2) will be assessed as a measure of effectiveness of risk minimization measures.

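### The testing outcome counts tests done before the reaction and, in Group 2, before the revised SIP, so the pre/post difference cannot serve as the measure of SIP effectiveness

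*Protocol*

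**What the plan says.** - **Purpose.** Protocol section 8 sets two aims: to determine the prevalence of testing among patients with a significant reaction, and to compare the two 3-year periods. Of the comparison it says the difference "will be assessed as a measure of effectiveness of risk minimization measures".
- **Groups.** Section 9.7.1 assigns patients by reaction onset date. Group 2 is "Patients with hypersensitivity/anaphylactic reaction event onset date from 01 October 2015 to 30 September 2018".
- **Outcome.** Section 9.7.2 counts a valid IgE, IgG, complement or tryptase result where "the test date is after the alglucosidase alfa treatment start date through the end of the period cutoff". The two cutoffs are simply the closing dates of the two study periods.
- **Same definition elsewhere.** The synopsis states "The outcome will be the history of any immunology testing since treatment start" and describes the laboratory source as recording "routine performance of immunology testing in the Genzyme Clinical Specialty Laboratory database since treatment start". Section 9.2 asks for the "full history of immunology testing since initiation of treatment with alglucosidase alfa". Section 9.3 lists testing since treatment start. The definition is deliberate, not a slip in one section.
- **Analysis.** Section 9.7.5 gives the prevalence per group, the difference with a 95% confidence interval, and splits by test type, age, gender and country. None of these restricts tests by date relative to the reaction. The limitations in section 9.9 do not mention the point.

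**The concern.** Group membership depends on when the reaction happened, but the outcome does not. A test that precedes the reaction cannot have been prompted by it, and a test that precedes distribution of the revised SIP cannot have been prompted by the SIP. Both kinds still make the patient a Yes.

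Two things are at stake in the effectiveness comparison. First, patients tested before their reaction are Yes whatever the physician does afterwards, so they carry no information on a change in practice and shrink the difference. A SIP that works could look ineffective. Second, if the share tested beforehand differs between the periods for unrelated reasons, such as different time on treatment, that imbalance enters the difference and is read as an effect, or hides one.

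**Working it through.** **The plan's own figures.** The only computed figures are the intervals in Table 3 (section 9.5). For n = 100 and 75%: 0.75 ± 1.96 × √(0.75 × 0.25 / 100) = 0.75 ± 0.085, or 66.5% to 83.5%, as printed. The other cells also reproduce, apart from a 0.1-point rounding difference in one upper limit (n = 50, 95%). The arithmetic is not at fault; the issue is what is being counted.

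**Model.** Let b be the share of a group with a valid test before the reaction, and q the probability of a test after it. Take q to be the same whether or not the patient was tested earlier. Under section 9.7.2 the observed prevalence is

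P = b + (1 - b) × q.

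With equal b in both groups, P2 - P1 = (1 - b) × (q2 - q1).

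**Dilution.** The protocol gives no values for b or q and assumes no number of patients, so these inputs are assumptions: q1 = 50%, q2 = 70% (true difference 20 points) and 100 patients per group, a size that Table 3 tabulates. The interval is the normal approximation planned in section 9.7.5: difference ± 1.96 × √[(P1(1 - P1) + P2(1 - P2)) / 100]. Power is for a two-sided 5% test of two proportions with pooled variance under the null; the protocol plans no test, so it is only a gauge.

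| b in both groups | P1 | P2 | Observed difference (95% CI half-width), points | Power |
|---|---|---|---|---|
| 0% | 50% | 70% | 20 (± 13.3) | 83% |
| 25% | 62.5% | 77.5% | 15 (± 12.5) | 64% |
| 50% | 75% | 85% | 10 (± 11.0) | 42% |
| 75% | 87.5% | 92.5% | 5 (± 8.3) | 22% |
| 90% | 95% | 97% | 2 (± 5.4) | 11% |

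Example for b = 50%: P1 = 0.5 + 0.5 × 0.5 = 0.75; P2 = 0.5 + 0.5 × 0.7 = 0.85; half-width 1.96 × √[(0.1875 + 0.1275) / 100] = 0.110.

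**Unequal prior testing** (also assumed values).
- No change after the reaction (q = 50% in both), b = 50% against 70%: P1 = 75%, P2 = 0.7 + 0.3 × 0.5 = 85%. A 10-point difference appears with no effect.
- True rise from 50% to 70%, b = 60% against 40%: P1 = 0.6 + 0.4 × 0.5 = 80%, P2 = 0.4 + 0.6 × 0.7 = 82%. A 20-point effect shows as 2 points.

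**A wording point in the same rule.** Section 9.7.2 says a patient qualifies "if one of the two conditions is met". Taken literally, a valid result at any date is enough and the date window does not bind. The note that follows implies that both conditions were meant. The concern holds on either reading.

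**The case against.** **The analyses are descriptive, and ever-tested prevalence is a legitimate quantity.** This stands for the first aim in section 8. It does not cover the second, because sections 8 and 9.7.5 commit to a between-period difference with an interval and section 8 gives it an effectiveness meaning. A reader might infer that the study cannot answer its question at all; that goes too far.

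**A reader might infer that the bias favours the SIP**, because the Group 2 cutoff is 1126 days (3.08 years) later and the outcome accumulates from treatment start. With an assumed 0.2 background tests per patient-year and 4 years of treatment, 1 - exp(-0.8) = 55.1%. Adding 1 to 3.08 years gives 63.2% to 75.7%, an apparent gain of 8 to 21 points. The documents do not support this. Groups are set by onset date in two 36-month windows, each closing at its own cutoff. If time from treatment start to reaction is distributed alike in both groups, the added history is zero and so is the gain. Extra history arises only if Group 2 patients have been treated longer, which the protocol does not say; section 9.7.4 would show it. At the interim reports Group 2 has one or two years of accrual against three, which would tend to work against the SIP.

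**A reader might also infer a ceiling from routine testing.** Section 9.5 says the prevalence is unknown and tabulates 50% to 95%. The synopsis phrase on routine performance may simply mean testing in ordinary practice.

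**The protocol does not reproduce the SIP's testing advice, so anchoring to the reaction presumes what the SIP asks for.** This is a fair caution and a reason to keep the ever-tested summary. But the protocol itself frames the target as testing in patients who experience reactions, and a test before the revised SIP cannot reflect it under any reading.

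**Conclusion.** The concern holds for the effectiveness comparison and not for the descriptive aim. Nothing in the protocol restricts tests to those after the reaction or, in Group 2, after 01 October 2015, and no planned analysis corrects for it.

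With equal prior testing, the difference is diluted by the factor (1 - b), given the assumption that post-reaction testing does not depend on earlier testing. With unequal prior testing, the bias can run either way. The point figures above are illustrations on assumed b, q and n; the documents fix neither the size nor the direction. What needs no assumption is that a Group 2 patient tested only before the reaction and before the revised SIP is scored as a post-SIP success.

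**What to change.** For the pre/post comparison in sections 9.7.2 and 9.7.5, define the outcome as a valid test dated on or after the onset of the patient's first qualifying reaction in that period, within a window whose length is fixed in advance and identical in both groups.

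State one rule, applied alike to both groups, for reactions whose window runs past the period cutoff: for example, exclude them or use a time-to-test estimate. Simply letting Group 1 windows run on past 31 August 2015 would carry them into the SIP distribution, which Table 2 shows from 14 September 2015.

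Keep any test since treatment start as a descriptive summary, report tests before onset separately by group, and align the synopsis and section 9.3. In 9.7.2, state that both conditions must be met.

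The cost is protocol wording and one derived date difference. Onset and test dates are already required, and section 9.7.4 already uses first onset within the period. The reported prevalence will be lower, and some patients or follow-up near each cutoff will be lost. The change does not settle exposure to the SIP itself: Table 2 lists 12 of 25 countries as still awaiting local approval at 02 December 2015, after Group 2 opens.

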All patients available in the study population will be considered for the analysis. No assumption will be made on the expected number of patients.

Data analysis

The primary analysis population will be patients with spontaneously reported significant hypersensitivity/anaphylactic reaction while treated with alglucosidase alfa treatment course in countries in Europe. The analyses will be descriptive and will be made on all patients available in the databases at time of each analysis.

The prevalence of testing will be provided for each period (3-year period before and 3-year period after implementation of the revised SIP). The difference in prevalence rate between two groups will be calculated, with corresponding 95% confidence interval calculated based on normal approximation of two proportions.

The results will be displayed by 3-year period before and after the implementation of revised SIP and by age, gender and country in Europe when appropriate.

Milestones

Annual analyses will be conducted over a 3-year period starting one year after implementation of the revised SIP in Europe. The implementation of the revised SIP may be started from 01 September 2015 after completion of pre-updated SIP data collection.

The first report will be prepared in December 2016, based on data gathered up to one year after implementation of the revised SIP (from 01 October 2015 to 30 September 2016) and will also include results for the 3-year period before implementation of the revised SIP (from 01 September 2012 to 31 August 2015).

The second report prepared in December 2017 will add data gathered in the second year after implementation of the revised SIP (from 01 October 2016 to 30 September 2017) and the final report prepared in December 2018 will include cumulative data for both periods (from 01 September 2012 to 31 August 2015 and from 01 October 2015 to 30 September 2018).

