12 PLANS FOR DISSEMINATING AND COMMUNICATING STUDY RESULTS

Annual interim reports and a final report will be submitted to EMA.

The first report will be prepared in December 2016, based on data gathered up to one year after implementation of the revised SIP and will also include results for the 3-year period before implementation of the revised SIP.

The second report prepared in December 2017 will add data gathered in the second year after implementation of the revised SIP year and the final report prepared in December 2018 will include cumulative data for both periods.

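### Test capture stops on the last day of each reaction-onset window, so late reactions have little time for a test afterwards, and the interim pre/post percentages are not comparable

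*Protocol*

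**What the plan says.** Protocol section 9.7.1 forms the groups by reaction onset. Group 1 (pre-SIP) is "Patients with hypersensitivity/anaphylactic reaction event onset date from 01 September 2012 to 31 August 2015". Group 2 (post-SIP) is "Patients with hypersensitivity/anaphylactic reaction event onset date from 01 October 2015 to 30 September 2018".

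Section 9.7.2 sets the time limits for a test to count: "the test date is after the alglucosidase alfa treatment start date through the end of the period cutoff". The same sentence names the cutoffs, "through the end of the period cutoff (31 August 2015 for Group 1 and 30 September 2018 for Group 2"), and these are the days on which the two onset windows close. A patient with no qualifying test is coded No, and the section concludes that the endpoint has no missing data.

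The synopsis (Milestones) makes the first report "based on data gathered up to one year after implementation of the revised SIP (from 01 October 2015 to 30 September 2016"), and that report "will also include results for the 3-year period before implementation of the revised SIP (from 01 September 2012 to 31 August 2015"). The second report "will add data gathered in the second year after implementation of the revised SIP (from 01 October 2016 to 30 September 2017"). The final report covers both full periods. Section 12 sends the interim reports and the final report to EMA. Section 9.7.2 gives no Group 2 cutoff for the interims.

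**The concern.** Because the onset window and the test window close on the same day, the time available for a test after the reaction depends on when in the window the reaction fell. A reaction on the first day has about three years and one on the last day has none. Coding the remainder as No turns this administrative truncation into non-testing. Section 9.9 does not list it among the limitations.

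At the interims the truncation is also unequal between groups, because a short post-SIP onset window stands beside the full pre-SIP one. The two interim reports could then suggest that testing fell after the revised SIP when behaviour had not changed. As the post-SIP window lengthens from report to report, the percentage would rise for the same reason, and that rise could be read as a delayed effect of the SIP.

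**Working it through.** **The plan's own figures.** The protocol has none on this point. Its only computed figures are the precision intervals in Table 3. For n = 100 and 75%, 0.75 ± 1.96 × √(0.75 × 0.25 / 100) gives 66.5% to 83.5%, as printed. That half-width of 8.5 points covers sampling error only, not the effect examined here.

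**Reading used.** The two conditions in section 9.7.2 are taken as joint. The text says that meeting one is enough, which read literally would make the date limit optional. That wording needs separate repair.

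**Step 1: window lengths**, from the dates in sections 9.7.1 and 4. With onsets uniform over a window of T months (an assumption), mean time from reaction to cutoff is T/2, and the share with under 3 months is 3/T.

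| Window | Days | Months | Mean time after reaction (months) | Under 3 months |
|---|---|---|---|---|
| Group 1 | 1095 | 36.0 | 18.0 | 8.3% |
| Group 2, interim 1 | 366 | 12.0 | 6.0 | 24.9% |
| Group 2, interim 2 (cumulative) | 731 | 24.0 | 12.0 | 12.5% |
| Group 2, final | 1096 | 36.0 | 18.0 | 8.3% |

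**Step 2: expected observed percentage.** Let p0 be the share already tested before the reaction, pe the eventual testing among the rest, and m the mean of an exponential delay in months. Then

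observed = p0 + (1 - p0) × pe × F, with F = 1 - (m/T) × (1 - exp(-T/m)).

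The protocol gives none of p0, pe or m. I take pe = 75%, m from 1 to 12 and p0 of 0, 50 and 80%, the same in both groups, so that behaviour does not change.

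Example with p0 = 0 and m = 3:
- T = 36: F = 1 - (3/36)(1 - exp(-12)) = 0.917, so 68.8% is observed.
- T = 12: F = 1 - (3/12)(1 - exp(-4)) = 0.755, so 56.6% is observed.
- Post minus pre at interim 1: -12.2 points.

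Post minus pre in points, interim 1 / interim 2:

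| Mean delay (months) | p0 = 0% | p0 = 50% | p0 = 80% |
|---|---|---|---|
| 1 | -4.2 / -1.0 | -2.1 / -0.5 | -0.8 / -0.2 |
| 3 | -12.2 / -3.1 | -6.1 / -1.6 | -2.4 / -0.6 |
| 6 | -20.0 / -5.9 | -10.0 / -3.0 | -4.0 / -1.2 |
| 12 | -23.7 / -8.7 | -11.8 / -4.3 | -4.7 / -1.7 |

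**Step 3: final report.** With T = 36 in both groups the artefact is 0.0 points in every cell. Eventual testing is still under-counted, by (1 - p0) × pe × (1 - F). For p0 = 0 this runs from 75.0 - 72.9 = 2.1 points (m = 1) to 75.0 - 51.2 = 23.8 points (m = 12). A true difference in pe is multiplied by (1 - p0) × F, where F runs from 0.97 (m = 1) to 0.68 (m = 12).

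**The case against.** The strongest objection is the look-back. The endpoint is the history of testing since treatment start, so a long-treated patient who reacts in late August 2015 may have years of countable time, and an earlier test already gives Yes. A reader might infer that late reactors have almost no chance of being counted as tested, or that the reports compare test-capture windows of 36 and 12 or 24 months. The documents support neither. Only the time after the reaction is short, and 36, 12 and 24 months are onset windows. This stands, and it is why the artefact is shown for several values of p0.

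A reader might also infer that the final comparison is biased. It is not: the onset windows are 1095 and 1096 days. Against the protocol's own definition, testing history by the cutoff, the final percentages are not understated. The under-count is relative to eventual testing after the reaction.

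Nor does the protocol say expressly that the between-group difference is computed at the interims. That is inferred from section 9.7, which speaks of each analysis, and from report 1 containing both periods. The analyses are descriptive, no interim decision rule is stated, and the unequal period lengths are visible to a reader. This lowers the stakes, but two percentages set side by side will still be compared.

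Finally, the net direction at interim is not fully settled. Group 2 patients react later in calendar time and may have a longer look-back, so p0 could be higher in Group 2 and offset part of the artefact. The calculation holds p0 equal.

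**Conclusion.** The concern holds in limited form. The rule leaves late reactions little or no post-reaction time, and at the interims it does so unequally: a mean of 6 and 12 months against 18, with about 25% and 12.5% against 8% of patients having under 3 months. Other things equal, this pushes the interim post-minus-pre difference down. Under the stated assumptions the shift is -4.2 to -23.7 points at interim 1 if none were tested before the reaction, -2.1 to -11.8 if half were, and -0.8 to -4.7 if 80% were. At interim 2 the ranges are -1.0 to -8.7, -0.5 to -4.3 and -0.2 to -1.7. These are ranges over unknown inputs, with no central estimate.

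The final contrast has no built-in difference if onset timing and testing delay are similar in the two periods. What remains there is an under-count of post-reaction testing in both groups and some dilution of a true difference. The change should be made, but the main final comparison does not fail without it.

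**What to change.** Keep the since-treatment-start history as defined. For the pre/post comparison at every report, add the proportion tested within the same fixed number of days W after the first in-period reaction (for example W = 90, with 30 and 180 as sensitivity analyses). Limit it to patients whose onset is at least W days before the cutoff. Every patient then has equal follow-up, and the artefact is zero at each report.

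Excluding late onsets is safer than extending the Group 1 look-up past 31 August 2015, because the earliest dated distribution of the revised SIP in Table 2 is 14 September 2015.

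Write the interim Group 2 cutoffs, 30 September 2016 and 30 September 2017 as in the synopsis, into section 9.7.2.

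The cost is one extra derivation and some patients. With uniform onsets, W = 90 leaves out 90/1095 = 8.2% of a 36-month window, 90/731 = 12.3% of Group 2 at interim 2 and 90/366 = 24.6% at interim 1. W = 180 leaves out 180/366 = 49.2% at interim 1. Patients left out at an interim enter at the next report; those in the last W days of a full period stay out of this added analysis. If delays are long, a 90-day window also captures only part of eventual testing (about 63% of it at a mean delay of 3 months, 39% at 6), but the same part in both groups.
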